## 9.0 STUDY PROCEDURES

### 9.1 STUDY FLOW CHART

### 9.2 RECRUITMENT/SUBJECT IDENTIFICATION PROCEDURE

Subjects are assigned an identification code by study personnel. The identification code is a single letter (A, B, C, etc.) indicating the study site, followed by a double digit number starting with (01) and proceeding consecutively with each subsequent subject. All data forms identify the subject by this number only. All study data is confidential and kept in a secure location. The Subject ID is documented on [REDACTED].

### 9.3 INFORMED CONSENT

The Investigator or designated personnel obtains written Informed Consent from all qualified subjects prior to their enrollment in the study. The Investigator or designated staff explains the nature and purpose of the study to the subjects. Subjects read the EC or IRB approved Informed Consent, have the opportunity to ask questions, and then sign and date the approved Informed Consent. One copy is given to the subject, and the original is retained by the

Investigator in a secure location with the study files. If applicable for HIPAA requirements, the Investigator obtains the subject's authorization to use PHI under HIPAA guidelines by obtaining their signature on an additional authorization form. The subject is provided with one copy of this authorization form and the investigator retains the original.

#### 9.4 ENROLLMENT

Enrollment follows Informed Consent (see Section 9.3) but both may occur during the same visit. The Investigator confirms Inclusion and Exclusion Criteria (listed in Sections 8.1 and 8.2) and, if the subject fulfills the criteria, the Investigator completes the [REDACTED]. The clinician will be blinded to whether the subject is randomized to the test barrier or control barrier.

#### 9.5 METHOD OF ASSIGNING PATIENTS TO STUDY ARMS

Subjects are randomized to Arm 1 (test barrier) or Arm 2 (control barrier) and assigned either study barriers [REDACTED] via a randomized block design stratified by study site and arm. The control barrier material is [REDACTED], depending on the Investigator's standard of care and the subject's needs, and the test barrier material is [REDACTED].

Central randomization is performed within the EDC system [REDACTED]

#### 9.6 BLINDING

Site personnel and subjects are blinded to the assigned study barrier; test or control. Thus, when randomized, the investigator is directed to study barriers which are labeled [REDACTED].

#### 9.7 CONCOMITANT THERAPY

Pertinent concomitant therapy is documented on [REDACTED] and [REDACTED].

#### 9.8 SUBJECT VISITS AND EVALUATION METHODS

The subject is enrolled into the eight (8) week [REDACTED] comprised of the Initial [REDACTED] Visit, the Mid-[REDACTED] Visit, and the Final [REDACTED] Visit. If during the [REDACTED] the subject experiences a PSC, they are immediately moved into the four (4) week [REDACTED] which is comprised of a Mid-[REDACTED] Visit, and a Final [REDACTED] Visit. An extra visit at any point during the study may also be necessary. Procedures for each visit are [REDACTED] listed in [REDACTED]

[REDACTED]

[REDACTED]

[REDACTED]

#### 9.9 SUBJECT / CAREGIVER INSTRUCTIONS

Subjects receive [REDACTED] in each box of study barriers. The subject also receives [REDACTED] including a phone number in order to reach the Investigator or designee. Subject is instructed to call the Investigator if peristomal skin condition changes. The subject may need to attend an extra in-person visit. [REDACTED] [REDACTED] also points out the importance of noting anything that has changed about the peristomal skin, and use of barrier, accessories, or other treatments.

#### 9.10 COMPLIANCE

Site personnel and study subjects are expected to fully comply with the protocol and study procedures. If the site personnel or subjects deviate from the protocol at any point, [REDACTED] is completed. Sites are monitored for compliance. If a site is found to have multiple deviations, corrective action or re-training may be necessary.

#### 9.11 PROCEDURES FOR SUBJECT DISCONTINUATION

Subjects electing to discontinue from the study for personal or other reasons are required to return all study materials and may be requested to schedule a final evaluation visit. The discontinuation of any subject following the Initial [REDACTED] Visit is documented using [REDACTED].

#### 9.12 INVESTIGATOR RESPONSIBILITIES

It is the responsibility of the Investigator to follow applicable Good Clinical Practice Guidelines and regulations including compliance with the protocol, recruiting and enrolling of appropriate subjects, properly storing and accounting for study barriers, ensuring adequate medical care is provided to subjects, properly obtaining Informed Consent, properly reporting Adverse Events, and maintaining all study related documents for a minimum of 2 years once informed from the Sponsor that the study is officially closed. The Investigator is responsible for providing source documentation that verifies the inclusion/exclusion criteria has been sufficiently met.

#### 9.13 SPONSOR RESPONSIBILITIES

It is the responsibility of Hollister to oversee the overall conduct of the trial and verify study procedures are adhered to by the Investigator. Hollister may transfer any or all trial-related duties and functions to a CRO, but the ultimate

responsibility for the quality and integrity of the study data resides with the sponsor.

## 10.0 ADVERSE EVENTS

### Anticipated Adverse Events

There is a small possibility that the subject may experience low level irritation of the peristomal skin. [REDACTED]

[REDACTED] Moderate or severe irritation is an anticipated Adverse Event.

### Unanticipated Events

An unanticipated adverse event occurs when the nature, severity or frequency of the event is not consistent with the known or foreseeable risk of the anticipated adverse events associated with the study barrier or procedures involved with this research.

### Serious Adverse Events

A serious adverse event is one that results in death, results in life-threatening illness or injury, requires in-patient hospitalization or prolongation of hospitalization, results in medical intervention to prevent permanent impairment, or results in permanent impairment of body structure or function. There are no serious adverse device events anticipated in this study.

### Handling of Adverse Events

Upon study enrollment, all subjects are informed to notify the Investigator immediately if they experience any study-related problems. The Investigator will determine if an adverse event has occurred and if it was related to the study barrier and the stoma and/or skin around the stoma. Adverse events are documented on [REDACTED] within the EDC system. The Investigator indicates if the adverse event is related to the study barrier by marking "possibly", "probably", or "definitely" on the Adverse Event Form. The Investigator also indicates if the Adverse Event is related to the stoma and/or peristomal skin. Subjects who report health problems may be directed to seek care from their healthcare provider or emergency room as appropriate.

All Adverse Events are followed to determine resolution [REDACTED] by the Investigator and the Adverse Event form is updated to indicate date of resolution. If at any point, the Investigator determines the subject should no longer remain on the study barrier, the subject should be discontinued from the study.

### Reporting of Adverse Events

Unanticipated device events and serious adverse events must be reported by the Investigator through the EDC system [REDACTED] by documenting on [REDACTED].

Serious adverse events must be reported to the Ethics Committee or Institutional Review Board, if appropriate, [REDACTED] or according to the Investigative site's Standard Operating Procedures.

## 11.0 DATA MANAGEMENT

It is the responsibility of the Investigator to ensure the completeness and accuracy of the Case Report Forms. It is the responsibility of the Investigator and the monitor to resolve any data queries recorded in the CRFs. All attachments are collected by the Sponsor except [REDACTED]

The Sponsor implements edit checks on the eCRF to enforce data entry guidelines, data consistency, and compliance to the protocol and regulatory requirements. The Investigator or designee is responsible for entering study data on the eCRFs, including data from the Quality of Life Questionnaire paper form completed by the subject during the visit. The Sponsor tracks eCRFs and reviews them for completeness, the presence of mandatory values, consistency, and dated electronic signatures. The Sponsor generates data clarification queries during the review process to ensure data quality. Once the Investigator or designee have provided acceptable responses to the queries and implemented the changes on the eCRFs, the Sponsor closes the queries with the appropriate resolution status. At the end of the study, the database is locked and the data is released for reporting and statistical analysis.

All required signatures on the eCRF are provided electronically by the Investigator or designee. Access to the eCRF for data entry and signature is controlled by user identification and password, which are provided by the Sponsor or designee. Investigators and their personnel are trained, by Sponsor and/or a designated CRO, in the use of eCRFs and application of electronic signatures before the start of the study.

Because it is extremely important to have proper data collection in a timely manner, the Investigator or designee and subjects complete the eCRFs on an ongoing basis. It is expected that the eCRFs for a particular subject are reviewed and completed by the Investigator within [REDACTED] of the subject's completion of the visit.

A limited supply of paper CRFs are provided to the site and can be used to collect data in the event of a loss of power or internet connection. Once power or internet connection is restored, the Investigator or designee enters the data into the EDC system and retains the original source documents in the study binder for monitoring.

## 12.0 STATISTICAL METHODS

### 12.1 ANALYSIS PRINCIPLES

All tests of the effect of treatment on outcome will be conducted for [REDACTED] the intent-to-treat population [REDACTED]. The analyses datasets will include data from randomized subjects only; subjects who are not randomized (i.e. screen failed) will be excluded from analysis.

### 12.2 ANALYSIS POPULATIONS

#### Intent-to-treat (ITT)

The ITT population will consist of all enrolled subjects who have been randomized to a study arm. Subjects will be analyzed in the arm to which they were randomized regardless of whether they received the assigned treatment and irrespective of any protocol deviations or violations.

[REDACTED]

[REDACTED]

### 12.3 INCOMPLETE FOLLOW-UP AND MISSING DATA

In the event that a subject does not complete the full eight weeks of the [REDACTED], or in the event of a PSC the full four weeks of the [REDACTED], the complete set of data available for that subject prior to loss-to-follow-up will be used for analysis. If there is missing data, there will be no imputation performed.

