### 12.4 COVARIATE ADJUSTMENT

The primary statistical analysis of total cost of care will be adjusted for, obesity (defined via BMI), ostomy type, stomal age (defined as weeks after surgery), and presence of a hernia. This is to account for the potential variability in the data induced by these covariates. All other analyses will be unadjusted.

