## 13.0 STATISTICAL ANALYSIS

### 13.1 ANALYSIS OF PRIMARY OBJECTIVE

Total cost of care is defined as all stoma related costs accrued through the duration of the study period. Health care resource utilization data collected to support this objective includes treatments related to stoma and/or PSCs (topical medications, clinic visits, accessory use, etc.), social impact of stoma and/or PSCs (e.g. missed work/appointments), hospitalizations, ER visits, physician/clinic visits, ostomy-related medication use and therapies, and barrier utilization (not including pouch utilization). [REDACTED]

[REDACTED] A corresponding country specific unit cost or reasonable estimate (when data is not available) will be assigned to each of the health care resource units listed above. Total cost of care will be calculated by multiplying the units of health care resources by the corresponding country specific resource unit cost and then summing costs across the study period.

The primary objective will be analyzed via an analysis of covariance (ANCOVA) model comparing the mean daily total cost of care between the treatment ([REDACTED]) and control ([REDACTED]) arms. The model will be adjusted for the covariates listed in Section 12.4, site location, and relevant demographic variables. Formally, the null and alternative hypotheses being evaluated are:

- a) Null: No difference in the mean total cost of care for 12 weeks between [REDACTED] and control i.e.  $H_0: \mu_{Test} = \mu_{Control}$  vs.
- b) Alternative: The mean total cost of care for 12 weeks for [REDACTED] is not equal to that of the control i.e.  $H_A: \mu_{Test} \neq \mu_{Control}$ .

[REDACTED]

[REDACTED]

3. Given assumptions 1 and 2, this results in a difference in mean total cost of care for the [REDACTED] and control arms of [REDACTED].
4. Using Meisner's costs of PSC according to level of severity [REDACTED] for 50% of the population, the estimate of the standard deviation for total cost of care is [REDACTED]

Using the estimates above the sample size required for to achieve 80% power with a 2.5% type 1 ( $\alpha$ ) error would be 72 per arm completed for the primary endpoint and 93 completed per arm for the secondary endpoint. In order to cover both primary and secondary endpoints, an initial sample size of 93 completed per arm was chosen. Based on the findings of the first interim analysis with 92 subjects [REDACTED] the sample size has been increased to 105 subjects per arm.

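### The ban on imputation in 12.3 does not fit a primary ANCOVA on all randomised subjects: a missing covariate drops the subject, and the scoring of missing utilisation is left open

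*Combined protocol and SAP*

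**What the plan says.** All references are to the combined protocol and SAP.

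- **Population.** Section 12.1 begins "All tests of the effect of treatment on outcome will be conducted for" and, around redacted words, names the intent-to-treat population. Section 12.2 defines it: "The ITT population will consist of all enrolled subjects who have been randomized to a study arm".
- **Missing data.** Section 12.3 has two rules. For early leavers, "the complete set of data available for that subject prior to loss-to-follow-up will be used for analysis". For everything else, "If there is missing data, there will be no imputation performed".
- **Endpoint.** Section 13.1 builds total cost by "multiplying the units of health care resources by the corresponding country specific resource unit cost and then summing costs across the study period". A missing unit cost may be replaced by a reasonable estimate. No visible text gives a matching rule for a missing count of units.
- **Model.** The primary analysis is an "analysis of covariance (ANCOVA) model comparing the mean daily total cost of care". Section 12.4 lists "obesity (defined via BMI), ostomy type, stomal age (defined as weeks after surgery), and presence of a hernia", and 13.1 adds further terms: "The model will be adjusted for the covariates listed in Section 12.4, site location, and relevant demographic variables". The hypotheses in 13.1 are written for total cost over 12 weeks.

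The visible text contains no item-level rule for unknown utilisation, no denominator for daily cost, no rule for a missing covariate and no missing-data sensitivity analysis.

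**The concern.** An ANCOVA uses only subjects with a value for the outcome and for every covariate. If nothing may be imputed, a randomised subject with one missing covariate is not in the primary test, and neither is a subject with no cost data after enrolment. The population in 12.2 and the rule in 12.3 cannot both be honoured once any model variable is missing.

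The cost sum raises a second problem. A missing count of units can be skipped, which amounts to costing it at zero, or it can make the subject's total missing. The first understates cost; the second removes the subject. The two choices can give different treatment effects, and the visible plan does not choose.

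The missingness may also be related to outcome. Section 8.4 lists adverse events among the reasons for discontinuation. Section 10.0 names skin irritation as the anticipated event and provides for discontinuation of a subject judged unfit to stay on the barrier. Section 4.0 treats skin complications as the driver of cost. Utilisation is collected at study visits (7.0), so one missed visit can leave a whole interval unknown.

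**Working it through.** **Inputs.** From 13.1: 80% power, 2.5% type 1 error, 72 completed per arm for the primary endpoint, 93 completed per arm for the secondary, later raised to 105 per arm. The difference and standard deviation are redacted, so 72 cannot be reproduced independently; it can only be inverted. The sample-size sentence does not give the sidedness of the 2.5%. I take it as two-sided, to match the alternative in 13.1, and show one-sided as well. All missing rates below are assumptions.

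**Step 1: effect implied by 72 per arm.** d = sqrt[2(z_alpha + z_power)² / n].
- Two-sided: sqrt[2(2.241 + 0.842)² / 72] = 0.514.
- One-sided: sqrt[2(1.960 + 0.842)² / 72] = 0.467.

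**Step 2: power with nobody lost.** Power = Phi[d·sqrt(n/2) − z_alpha]. At 105 per arm this is 93.1% (two-sided) or 92.3% (one-sided).

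**Step 3: power after losing 15% of 105.** n = 105 × 0.85 = 89.25, and sqrt(89.25/2) = 6.680.
- Two-sided: Phi(0.514 × 6.680 − 2.241) = Phi(1.19) = about 88%.
- One-sided: Phi(0.467 × 6.680 − 1.960) = Phi(1.16) = about 88%.

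Power on this effect falls below 80% only when fewer than 72/105 = 68.6% remain, that is, after a loss of about 31%.

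**Step 4: how missing covariates add up.** If each of the four covariates in 12.4 is missing independently with probability m, the complete share is (1 − m)^4.

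| m per covariate | Complete share | Left of 105 | Power, two-sided | Power, one-sided |
|---|---|---|---|---|
| 1% | 96.1% | 100.9 | 92.0% | 91.2% |
| 2% | 92.2% | 96.8 | 90.9% | 90.1% |
| 5% | 81.5% | 85.5 | 86.8% | 86.3% |
| 10% | 65.6% | 68.9 | 78.1% | 78.2% |

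The unnamed demographic variables could add to these losses.

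**Step 5: bias if missing items count as zero.** If a share s of an arm's cost is missing and nothing replaces it, the recorded mean is μ(1 − s). With no true effect, test minus control is μ(s_control − s_test). Set μ = 100 in control:

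| Missing share, control / test | Difference, no true effect | Difference, true effect −20 |
|---|---|---|
| 5% / 5% | 0 | −19 |
| 10% / 10% | 0 | −18 |
| 20% / 20% | 0 | −16 |
| 5% / 10% | −5 | −23 |
| 10% / 5% | +5 | −14 |
| 10% / 20% | −10 | −26 |

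Equal missingness shrinks a true difference. Unequal missingness creates or distorts one, by the gap in shares times mean cost.

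**The case against.** The case for leaving the plan alone has several sound parts.

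- **Early leavers are kept.** Section 12.3 uses their data, and the endpoint is a daily cost, so short follow-up alone need not bias the result if the denominator is days observed. This stands, but the visible text does not give the denominator, and the 12-week hypotheses leave it in doubt. A daily average also does not repair a gap within the observed period, where the days count and the missing item adds nothing.
- **Covariates may be nearly complete.** Ostomy type and stomal age correspond to inclusion criteria 2 and 3, which 9.12 requires source documents to support, and 11.0 provides for eCRF review and queries on mandatory values. This stands. Loss through the named covariates may be small, and nothing in the plan supports any particular rate.
- **Available-case analysis within an ITT set is common.** True. Section 12.2 says who belongs to the set and how they are grouped. The complaint is that the rule prevents all of them from being analysed.
- **Redaction.** Text after the utilisation list in 13.1 and after the ITT definition in 12.2 is blacked out. Rules may sit there, so absence is claimed only for the visible text.

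Two stronger readings should be resisted. A reader might infer that the plan scores missing utilisation as zero. It nowhere says so; the total could equally become missing. A reader might also take 80% as the starting power and find 77.7%, 75.3% and 72.6% after losses of 5%, 10% and 15%. That arithmetic is right, but 13.1 attaches 80% power for the primary endpoint to 72 completed per arm, not to 105. The 80% quoted with 105 in 13.5 is conditional power, and the effect and endpoint behind it are not visible.

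**Conclusion.** The point holds and the text should be changed. A blanket ban on imputation cannot deliver a primary ANCOVA on all randomised subjects once a model variable is missing, and the visible plan leaves the scoring of missing utilisation open.

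The size is conditional. On the effect implied by 72 per arm, power at 105 stays near 88% after a 15% loss, so power is the lesser issue. If the interim data point to a smaller effect, the margin is thinner; the documents do not show it. The main exposure is bias in the cost comparison: zero-filling would give a false difference of about 5% of mean cost for each 5-point gap between arms in missing cost share, and removing subjects with incomplete cost could select on outcome. Neither can be shown to occur, because missing rates are not given.

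**What to change.** Amend 12.3, with the wording written by staff blinded to arm-level results and preferably before the further interim analysis in 13.5:

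1. Fill missing baseline covariates by a simple rule that ignores arm (mean, mode or a missing category), so that no randomised subject with cost data is dropped.
2. Score only confirmed non-use as zero, never unknown utilisation. Define daily cost as cost divided by days observed.
3. Support the ITT cost analysis with multiple imputation of missing utilisation, done by arm, using site, the 12.4 covariates, PSC status and observed cost. Report it with the available-data analysis.
4. Add a delta-adjusted analysis to probe departures from missing at random. The available-data analysis cannot do this, because it rests on a comparable or stronger assumption about missingness.

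The cost is some programming, reliance on missing at random in the imputed analysis, and a documented blinded amendment. The last matters because the first interim analysis has already been used to raise the sample size.

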### 12.4 COVARIATE ADJUSTMENT

The primary statistical analysis of total cost of care will be adjusted for, obesity (defined via BMI), ostomy type, stomal age (defined as weeks after surgery), and presence of a hernia. This is to account for the potential variability in the data induced by these covariates. All other analyses will be unadjusted.

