### 5.2 SECONDARY OBJECTIVE

The secondary objective of the study is to compare incidence of PSCs in subjects using [REDACTED] to subjects using the control barriers [REDACTED].

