## 8.0 STUDY SUBJECTS

### 8.1 INCLUSION CRITERIA

1. At least 18 years of age
2. Have a colostomy, ileostomy, or urostomy
3. Less than or equal to 12 weeks post-op from stoma creation or stoma relocation

4. Have normal peristomal skin (as defined by a DET score = 0 or a DET score > 0 due to normal post-operative healing and/or scar tissue) at study enrollment  
Note: Subjects with suture granulomas or any other peristomal skin complication are not eligible for enrollment.
5. Able to provide an informed consent for study participation
6. Willing to follow protocol procedures, including attending in-person visits, as demonstrated by signing the informed consent

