### 12.5 MULTI-CENTER ADJUSTMENT

Multiple centers/sites will contribute data to this study. Given the variance in standard of care between sites, the primary analysis will be adjusted for site variability. This will be done by including a categorical site covariate in the primary analysis model. The secondary [REDACTED] objectives will not be adjusted for site.

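### PSC incidence is compared unadjusted although the prognostic factors are already collected, which forgoes a modest gain in power if they predict PSC

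*Combined protocol and SAP*

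**What the plan says.** Section 5.2: "The secondary objective of the study is to compare incidence of PSCs" between the test and control barriers.

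Section 8.1 admits three stoma types ("Have a colostomy, ileostomy, or urostomy") and sets the entry window as "Less than or equal to 12 weeks post-op from stoma creation or stoma relocation", with no lower limit given.

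Section 12.4 adjusts the primary cost analysis for "obesity (defined via BMI), ostomy type, stomal age (defined as weeks after surgery), and presence of a hernia". Its reason is: "This is to account for the potential variability in the data induced by these covariates". It then says: "All other analyses will be unadjusted". Section 12.5 adds that the secondary "objectives will not be adjusted for site".

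Section 9.5 stratifies randomization by site (and, as worded, by arm). Ostomy type and stomal age are not listed as strata.

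Section 13.1 gives 72 completers per arm for the primary endpoint and 93 for the secondary, at 80% power and a 2.5% type 1 error; the size was later raised to 105 per arm. Section 12.6 applies a Bonferroni correction to the secondary endpoint. Section 12.3 rules out imputation.

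**The concern.** The plan treats four baseline factors as worth adjusting for in the cost analysis and gives no readable reason for treating PSC incidence differently. Section 4.0 expects the barrier to lower cost by reducing PSCs, so it is plausible, though not shown, that some of the same factors bear on PSC onset.

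Stomal age may also affect how the endpoint is classified. Sections 2.0 and 7.0 do not count a DET score above 0 that is due to normal post-operative healing, so the judgement depends partly on how recent the surgery is.

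Two things are at stake. If the factors are prognostic, an unadjusted test has less power than an adjusted one. And because the listed strata do not include them, neither the readable design nor the analysis corrects a chance imbalance in them. PSC incidence is the endpoint behind the initial 93 per arm, so efficiency on it matters.

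**Working it through.** **1. The plan's own figure.** The assumed PSC rates are redacted, so 93 per arm cannot be confirmed. It can only be inverted, using

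n = [z_α √(2p̄(1−p̄)) + z_β √(p₁(1−p₁)+p₂(1−p₂))]² / (p₁−p₂)²

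- 50% vs 30%, two-sided 5% (or one-sided 2.5%): (1.960 × 0.6928 + 0.8416 × 0.6782)² / 0.20² = 93.0.
- 50% vs 28%, two-sided 2.5%: (2.241 × 0.6898 + 0.8416 × 0.6720)² / 0.22² = 92.1, so 93.

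Both pairs fit, as do others such as 60% vs 37.5% at two-sided 2.5%. Bonferroni gives 0.05/2 = 0.025, but sidedness is not stated. The rates below are therefore assumptions.

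**2. Power at 105 per arm without adjustment.** For an effect with 80% power at 93, it is about 85% under either reading of alpha. The formula uses marginal rates, which already average over case mix, so heterogeneity does not by itself pull power below plan.

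**3. Gain by effective sample size.** If the covariates explain a share R² of outcome variance, adjustment acts like n/(1−R²). At two-sided 2.5%:

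| R² | 105/(1−R²) | Power | Subjects per arm forgone (105 × R²) |
|---|---|---|---|
| 0 | 105 | 85.0% | 0 |
| 0.02 | 107.1 | 85.8% | 2.1 |
| 0.05 | 110.5 | 87.0% | 5.2 |
| 0.10 | 116.7 | 88.9% | 10.5 |

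**4. Gain by simulation, four factors, 105 per arm.** Assumed mix: ostomy type 40/45/15%, stomal age uniform over 0 to 12 weeks, obesity 30%, hernia 10%. With 50% vs 30% at two-sided 5% and a logistic Wald test, power rises as follows:

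- combined log-odds SD 0.45: 84% to 85%
- SD 0.64: 84% to 86%
- SD 0.96: 84% to 89%

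At two-sided 2.5%, with 50% vs 28.1% and SD 0.45, it goes from 85.2% to 86.0%. Repeating the exercise with the standardised risk difference, at either alpha, gives gains of about 1 to 6 points over SD 0.45 to 0.96 and no material loss when the factors are not prognostic.

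To judge these SDs: if the log-odds are roughly normal, the 10th-to-90th percentile odds ratio is exp(2 × 1.2816 × SD). That is about 3 at 0.45, 5 at 0.64 and 12 at 0.96.

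**5. Cross-check, ostomy type and stomal age only.** At 93 per arm, two-sided 2.5% and 50% control rate, the same odds ratio is assumed between stoma types and across the 12 weeks. Unadjusted vs adjusted power:

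- OR 1.5: 80.8% vs 81.0%
- OR 2: 79.6% vs 80.7%
- OR 3: 80.7% vs 83.8%
- OR 4: 81.2% vs 85.3%

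Monte Carlo error is about 0.6 points. Type I error was 2.0% to 2.2% unadjusted and 2.5% to 2.6% adjusted, against a nominal 2.5%.

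**6. Chance imbalance.** If one ostomy type makes up 45% of subjects (assumption), the SE of the between-arm difference in its share at 105 per arm is √(2 × 0.45 × 0.55/105) = 6.9 points. An imbalance of 10 points or more then occurs about 15% of the time (10/6.9 ≈ 1.46 SE). If PSC risk in that type differs by 20 points from the rest (assumption), a 10-point imbalance moves the PSC difference by 0.10 × 20 = 2 points. The SE of the PSC difference at 50% vs 30% is √((0.25 + 0.21)/105) = 6.6 points, so the shift is under a third of one SE.

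**The case against.** A reader might infer that the trial is underpowered for PSC, or that the unadjusted comparison is biased. The documents support neither. An unadjusted comparison of randomized arms is valid, and step 2 shows no shortfall against 80%. What is lost is efficiency relative to a better analysis.

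A reader might also take it as established that PSC risk depends on stoma type and time since surgery. No readable passage says so. Section 12.4 speaks only of potential variability, and for cost. Nor does the cost link settle it: under Section 13.1 cost includes barrier and accessory use, hospital and ER visits and missed work, which these factors could affect without any PSC. This objection stands, and it is why the point is conditional.

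Three practical objections carry some weight.

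- **Missing covariates.** With no imputation, subjects lacking one would drop out of the model. At 93 per arm, two-sided 5%, SD 0.45 and 5% of subjects affected (assumption), power is 79.9% unadjusted against 79.4% adjusted, so the gain is gone. The fix has to deal with this.
- **Timing.** One interim has been done and used to raise the sample size, so this is a mid-trial change needing EC/IRB approval under Section 16.0.
- **Site.** The four-factor model still omits the randomization stratum. A categorical site term may be unstable in a logistic model if there are many small sites. That is a separate choice, made in Section 12.5.

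Sections 13.2 to 13.4 are not readable, so a supportive adjusted analysis cannot be excluded, but Section 12.4 is explicit that analyses other than the primary are unadjusted.

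**Conclusion.** The point holds as a conditional, modest matter of efficiency. The plan leaves PSC incidence unadjusted for four factors that it must collect for the primary model. If they predict PSC, it forgoes power and leaves chance imbalance in them uncorrected.

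At 105 per arm the gain forgone is about 0 points with no prognostic effect, about 1 to 3 points at combined log-odds SD 0.45 to 0.64, and about 5 to 6 points only at SD 0.96, which is a very strong effect. These figures rest on assumed rates of 50% vs 28% to 30%, an assumed case mix, and prognostic strengths on which the documents are silent. The change is still worth making, because it needs no new data and costs almost nothing in power if the factors turn out not to matter.

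**What to change.** In Section 12.4, replace the sentence on unadjusted analyses, for the secondary endpoint, with a prespecified analysis:

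- Logistic regression of PSC (yes/no) on arm, ostomy type, stomal age at enrolment (continuous), obesity and hernia at enrolment.
- Report the covariate-standardised risk difference with its confidence interval, tested at the plan's Bonferroni-adjusted alpha. This keeps the marginal incidence comparison of Section 5.2.
- Report the unadjusted comparison alongside as supportive.
- Keep randomized subjects who lack a baseline covariate in the model, for example by a missing-category indicator or a simple baseline mean fill. State this as an explicit exception to the no-imputation rule in Section 12.3.

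Staff without access to results by arm should fix the wording by amendment before the additional interim described in Section 13.5 and before final unblinding.

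Cost: a small protocol/SAP amendment after one interim has already been done, and a slightly more complex headline analysis. No new data are needed.
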